### 13.3. EXPLORATORY EFFICACY

#### 13.3.1. EXPLORATORY EFFICACY VARIABLES & DERIVATIONS

##### 13.3.1.1. The Pittsburgh Sleep Quality Index (PSQI)

The PSQI assesses sleep quality during the past month and is to be completed as a once off assessment by subjects at the end of each annual Allergy Assessment Period. It consists of 19 self-rated questions and five completed by a bed-partner/roommate. Refer to [APPENDIX 2: Complete Questionnaires](#), for the complete questionnaire. For the self-rated questions there are four questions about bed and sleep times and 15 questions (each scored in one of four categories) that elicit the quality of sleep.

The range of values for questions five through 10 are all 0 to 3.

Questions one through nine are not allowed to be missing except as noted below. If these questions are missing then any scores calculated using missing questions are also missing. Thus it is important to make sure that all questions one through nine have been answered.

In the event that a range is given for an answer (for example, '30 to 60' is written as the answer to Q2, minutes to fall asleep), split the difference and enter 45.

The total PSQI and component scores (duration of sleep, sleep disturbance, sleep latency, day dysfunction due to sleepiness, sleep efficiency, overall sleep quality and need medications to sleep) are calculated from the questionnaire and the scoring instructions below:

Table 1 : Scoring Instructions		
Domain	Question (Q) Result or Algorithm	Analysis Value
Duration of Sleep	$Q4 > 7$	0
	$6 < Q4 \leq 7$	1
	$5 \leq Q4 \leq 6$	2
	$Q4 < 5$	3
Sleep Disturbance	$Q5b + Q5c + Q5d + Q5e + Q5f + Q5g + Q5h + Q5i + Q5j = 0$ NOTE: If Q5j-Other reason(s), is null or Q5j is null, set the value of Q5j to 0	0
	$Q5b + Q5c + Q5d + Q5e + Q5f + Q5g + Q5h + Q5i + Q5j \geq 1 \text{ and } \leq 9$	1
	$Q5b + Q5c + Q5d + Q5e + Q5f + Q5g + Q5h + Q5i + Q5j \geq 10 \text{ and } \leq 18$	2
	$Q5b + Q5c + Q5d + Q5e + Q5f + Q5g + Q5h + Q5i + Q5j \geq 19 \text{ and } \leq 27$	3
Sleep Latency	Step 1:	

Document: CP007A SAP.docx

Author: [name]

Version Number:

V 2.0

Version Date:

23 Feb 2017

Template No: CS\_TP\_BS016 – Revision 3

Reference: CS\_WI\_BS005

Effective Date: 01May2012

Copyright © 2012 Quintiles Transnational Corp. All rights reserved.

The contents of this document are confidential and proprietary to Quintiles Transnational Corp. Unauthorized use, disclosure or reproduction is strictly prohibited.

	If $0 \leq Q2 \leq 15$ then set $Q2 = 0$	
	If $15 < Q2 \leq 30$ then set $Q2 = 1$	
	If $30 < Q2 \leq 60$ then set $Q2 = 2$	
	If $Q2 > 60$ then set $Q2 = 3$	
	Step 2:	
	$Q5a + Q2 = 0$	0
	$1 \leq Q5a + Q2 \leq 2$	1
	$3 \leq Q5a + Q2 \leq 4$	2
	$5 \leq Q5a + Q2 \leq 6$	3
Day Dysfunction Due to Sleepiness	$Q8 + Q9 = 0$	0
	$1 \leq Q8 + Q9 \leq 2$	1
	$3 \leq Q8 + Q9 \leq 4$	2
	$5 \leq Q8 + Q9 \leq 6$	3

### 13.3.1.2. 6-Question Asthma Control Questionnaire (ACQ) Score

Asthmatic subjects are to complete the 6-Question ACQ at the end of each annual Allergy Assessment Period as a one off assessment. Refer to [APPENDIX 2: Complete Questionnaires](#), for the complete questionnaire.

The six ACQ questions are answered by the subject, stating how they have been in the past week with regards to five symptoms and the average daily use (the number of puffs/inhalations) of short-acting bronchodilator in the past week.

There is a 7 point scale (0 to 6) for each question where 0 represents optimum control and six represents the poorest control. The questions are equally weighted and the ACQ score is the mean of the six questions and therefore between 0 (totally controlled) and six (severely uncontrolled).

### 13.3.1.3. Work Productivity and Activity Impairment Questionnaire plus Classroom Impairment Questions: Allergy Specific (WPAI:CIQ-AS)

The WPAI:CIQ-AS is to be completed at the end of each annual Allergy Assessment Period and consists of nine questions. Refer to [APPENDIX 2: Complete Questionnaires](#), for the complete questionnaire.

The WPAI:CIQ-AS consists of seven domains calculated as follows:

- Percent work time missed due to allergy;  $Q3/Q2 \times 100$

Document: CP007A SAP.docx

Author: [name]

Version Number:

V 2.0

Version Date:

23 Feb 2017

Template No: CS\_TP\_BS016 – Revision 3

Reference: CS\_WI\_BS005

Effective Date: 01May2012

Copyright © 2012 Quintiles Transnational Corp. All rights reserved.

The contents of this document are confidential and proprietary to Quintiles Transnational Corp. Unauthorized use, disclosure or reproduction is strictly prohibited.

- Percent impairment while working due to allergy;  $Q4/10 \times 100$
- Percent overall work impairment due to allergy;  $((Q3/Q2) + [(1 - (Q3/Q2)) \times (Q4/10)]) \times 100$
- Percent class time missed due to allergy;  $Q7/Q6 \times 100$
- Percent impairment in the classroom due to allergy;  $Q8/10 \times 100$
- Percent overall classroom impairment due to allergy;  $((Q7/Q6) + [(1 - (Q7/Q6)) \times (Q8/10)]) \times 100$
- Percent activity impairment due to allergy;  $Q9/10 \times 100$

The outcomes are expressed as impairment percentages, with higher numbers indicating greater impairment and less productivity. If any questions within a domain are missing, the domain value will also be missing.

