#### Pittsburgh Sleep Quality Index

01. During the past month, what time have you usually gone to bed at night?
02. During the past month, how long (in minutes) has it usually taken you to fall asleep each night?
03. During the past month, what time have you usually gotten up in the morning?
04. During the past month, how many hours of actual sleep did you get at night? (This may be different than the number of hours you spent in bed.)
05. During the past month, how often have you had trouble sleeping because you...
  - a) Cannot get to sleep within 30 minutes
  - b) Wake up in the middle of the night or early morning
  - c) Have to get up to use the bathroom
  - d) Cannot breathe comfortably

---

Document: CP007A SAP.docx  
Author: [name]

Version Number: V 2.0  
Version Date: 23 Feb 2017

Template No: CS\_TP\_BS016 – Revision 3  
Effective Date: 01May2012

Reference: CS\_WI\_BS005

Copyright © 2012 Quintiles Transnational Corp. All rights reserved.

The contents of this document are confidential and proprietary to Quintiles Transnational Corp. Unauthorized use, disclosure or reproduction is strictly prohibited.

e) Cough or snore loudly

f) Feel too cold

g) Feel too hot

h) Had bad dreams

i) Have pain

j) Other reason(s), please describe How often during the past month have you had trouble sleeping because of this?

06. During the past month, how would you rate your sleep quality overall?

07. During the past month, how often have you taken medicine to help you sleep (prescribed or “over the counter”)?

08. During the past month, how often have you had trouble staying awake while driving, eating meals, or engaging in social activity?

09. During the past month, how much of a problem has it been for you to keep up enough enthusiasm to get things done?

10. Do you have a bed partner or room mate?

If you have a room mate or bed partner, ask him/her how often in the past month you have had...

a) Loud snoring

b) Long pauses between breaths while asleep

c) Legs twitching or jerking while you sleep

d) Episodes of disorientation or confusion during sleep

e) Other restlessness while you sleep; please describe

Work Productivity and Activity Impairment Questionnaire plus Classroom Impairment Questions:  
Allergy Specific

01. Are you currently employed (working for pay)? (If NO, check “NO” and skip to question 5.)

02. In general, how many hours per week do you usually work?

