03. During the past seven days, how many hours did you miss from work because of problems associated with your allergies? Include hours you missed because you were sick, times you went in late, left early, etc. because you were experiencing problems with your allergies. (Do not include time you missed to participate in this study.)

04. During the past seven days, how much did allergies affect your productivity while you were

---

Document: CP007A SAP.docx

Author: [name]

Version Number:

V 2.0

Version Date:

23 Feb 2017

Template No: CS\_TP\_BS016 – Revision 3

Reference: CS\_WI\_BS005

Effective Date: 01May2012

Copyright © 2012 Quintiles Transnational Corp. All rights reserved.

The contents of this document are confidential and proprietary to Quintiles Transnational Corp. Unauthorized use, disclosure or reproduction is strictly prohibited.

working? Think about days you were limited in the amount or kind of work you could do, days you accomplished less than you would like, or days you could not do your work as carefully as usual. If allergies affected your work only a little, choose a low number. Choose a high number if allergies affected your work a great deal.

05. Do you currently attend classes in an academic setting (middle school, high school, college, graduate school, additional course work, etc.)? (If NO, check “NO” and skip to question 9.)

06. In general, how many hours per week do you usually attend classes?

07. During the past seven days, how many hours did you miss from class or school because of problems associated with your allergies? (Do not include time you missed to participate in this study.)

08. During the past seven days, how much did allergies affect your productivity while in school or attending classes in an academic setting? Think about days your attention span was limited, you had trouble with comprehension or days in which you could not take tests as effectively as usual. If allergies affected your productivity at school or in class only a little, choose a low number. Choose a high number if allergies affected your productivity a great deal. (Cross a number.)

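### WPAI scoring makes overall impairment missing where the SAP's own formula already fixes it at 100%, and lets time missed and overall impairment exceed 100%

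*SAP*

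**What the plan says.** SAP 13.3.1.3 derives seven domains from the nine WPAI:CIQ-AS items. Three matter for work:

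- percent work time missed, Q3/Q2 × 100;
- percent impairment while working, Q4/10 × 100;
- percent overall work impairment, which adds to the share of time missed the remaining share multiplied by Q4/10.

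The classroom domains have the same form with Q6, Q7 and Q8 in place of Q2, Q3 and Q4. On the scale the SAP says: "The outcomes are expressed as impairment percentages, with higher numbers indicating greater impairment and less productivity". On incomplete items it says: "If any questions within a domain are missing, the domain value will also be missing".

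The item wording is in SAP Appendix 2. The work denominator, Q2, is "In general, how many hours per week do you usually work", and the class denominator, Q6, is "In general, how many hours per week do you usually attend classes". The work numerator, Q3, is "During the past seven days, how many hours did you miss from work because of problems associated with your allergies". Q4 asks "During the past seven days, how much did allergies affect your productivity while you were" working. There are two skips: a subject who is not employed goes to Q5, and one who attends no classes goes to Q9. Neither covers an employed subject or student who was absent for the whole week.

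SAP 13.3.2.3 summarises the scores descriptively, with no model or test.

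**The concern.** Two features of the rule give a wrong value for subjects with a very high share of time missed.

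First, a subject who worked no hours has no experience on which to answer a question about productivity while working, so a blank Q4 is a foreseeable response. The any-missing rule then discards an overall score that did not depend on Q4.

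Second, numerator and denominator refer to different periods: one particular week against a usual week. After a week with more hours due than usual, or an entry error, missed hours can exceed usual hours. The result is a share of time above 100%, which has no meaning.

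At stake is the accuracy of the descriptive summaries for a named exploratory objective, productivity (Protocol 2.3, SAP 2.3). The faults act at the top of the scale, where a few values can move a mean. Because the first removes values according to how high they are, it does not average out.

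**Working it through.** The SAP states no figure to reproduce here, so the check is to apply its formulas literally.

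**Inputs.** Formulas and missing-item rule from SAP 13.3.1.3; item definitions and skips from SAP Appendix 2. Write r = Q3/Q2.

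**Formula.** Overall = (r + (1 − r) × Q4/10) × 100.

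**At r = 1.** Overall = (1 + 0 × Q4/10) × 100 = 100% for every Q4 from 0 to 10. Q4 carries no information, but leaving it blank makes the score missing.

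**At r > 1.** Overall = (r − (r − 1) × Q4/10) × 100, which is above 100% for every Q4 below 10. Time missed is r × 100, always above 100%.

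| Q2 | Q3 | Time missed | Overall, Q4 = 0 | Overall, Q4 = 5 | Overall, Q4 = 10 | Overall, Q4 blank |
|---|---|---|---|---|---|---|
| 40 | 40 | 100% | 100% | 100% | 100% | missing |
| 40 | 48 | 120% | 120% | 110% | 100% | missing |
| 20 | 30 | 150% | 150% | 125% | 100% | missing |

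For the last row at Q4 = 5: 1.5 + (−0.5)(0.5) = 1.25, or 125%. The classroom domains behave identically with Q6, Q7 and Q8.

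**Effect of the first fault on a mean (assumed rates).** Let a fraction f of workers be fully absent with Q4 blank, and let the rest average 20%. The mean with them included is f × 100 + (1 − f) × 20; the plan reports 20.0%.

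- f = 1%: 1 + 19.8 = 20.8%
- f = 2%: 2 + 19.6 = 21.6%
- f = 5%: 5 + 19.0 = 24.0%

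**Effect of the second fault (assumed rates).** If the same fractions instead had Q2 = 20, Q3 = 30, Q4 = 5, each would score 125% rather than 100%. The mean would rise by f × 25, which is 0.25 points at 1% and 1.25 points at 5%. The two faults therefore pull in opposite directions.

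**Is it cured elsewhere?** SAP 7.3 refers missing efficacy data to SAP 13.1.3, which deals only with the daily Combined Score. Protocol 7.1 and SAP 4.1 require general data checks and no open queries before each snapshot, but state no WPAI range check. The SAP does write item-level exceptions elsewhere: for the PSQI (SAP 13.3.1.1), a null Q5j is set to 0. The WPAI has no counterpart.

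**The case against.** The strongest reply is that this is a rare edge case in a descriptive endpoint, and much of that stands.

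- **Such subjects remain visible.** A fully absent worker with Q4 blank still counts as 100% in time missed and still has activity impairment from Q9. Days off school or work are also summarised monthly (SAP 13.3.2.5). A reader might infer that the most affected subjects drop out of the analysis. They do not: they lose the overall score and impairment while working, and for the latter missing is reasonable.
- **The trigger is not documented.** No skip covers Q4, so an employed subject is asked to answer it, and any answer with Q3 = Q2 gives 100%. General cleaning may catch some entries, and the maximum is reported, so a value above 100% would show. This mitigates the faults but does not change the rule.
- **Bias toward no effect is not shown.** A reader might infer that the placebo arm loses more total absences and that the productivity difference shrinks. Assume 3% of placebo and 1% of active workers are fully absent, with all others at 20%. The true means are 22.4% and 20.8%. If every such Q4 is blank, 20% is reported in both arms. If half are blank, the reported means are (1.5 + 19.4)/0.985 = 21.2% and (0.5 + 19.8)/0.995 = 20.4%, a difference of about 0.8 points instead of 1.6. The scenario also places the whole treatment effect in total absence. Neither the rates nor that premise comes from the documents, values above 100% push the other way, and no formal comparison is planned.
- **Q3 = Q2 does not prove total absence.** Q2 is usual hours, so someone due 30 hours whose usual week is 20 could miss 20 and work 10. This stands as a caution for the remedy: an answered Q4 should be kept. It does not rescue the rule, because the SAP's formula returns 100% at Q3 = Q2 in any case.

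**Conclusion.** The point holds as a minor scoring error. A stated rule gives the wrong result in two situations: it returns missing where the formula already determines 100%, and it returns percentages above 100 where missed hours exceed usual hours. The first affects the two overall domains (work and classroom); the second affects those and the two time-missed domains. Impairment while working, impairment in the classroom and activity impairment are not misscored.

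The size is unknown because the documents give no frequency for either situation. The range of 0.8 to 4.0 points on a mean of 20% rests on assumed absence rates of 1% to 5%, Q4 blank for all of those subjects, and an average of 20% in everyone else. It describes the first fault alone; net direction cannot be stated once the second is counted. The endpoint is exploratory, so no primary or secondary conclusion depends on it.

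**What to change.** In SAP 13.3.1.3, add:

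1. Where Q3 ≥ Q2 > 0 and Q4 is blank, set overall work impairment to 100% and leave only impairment while working missing.
2. Query any record with Q3 > Q2. If the entry is confirmed, cap Q3/Q2 at 1 when computing time missed and overall impairment, and keep any answered Q4 for impairment while working.
3. Apply the same rules to Q7, Q6 and Q8.

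With these rules, Q2 = 40, Q3 = 40, Q4 blank scores 100% overall instead of missing. Q2 = 20, Q3 = 30, Q4 = 5, once confirmed, scores 100% time missed and 100% overall, with impairment while working kept at 50%. Querying before capping matters, because capping alone could turn an entry error into maximum impairment.

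The same edit could say what happens when Q2 or Q6 is zero, since the ratio is then undefined and the SAP is silent.

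The cost is a few sentences of SAP text, a small derivation change and a few data queries. No new data are needed, and no score with Q3 below Q2 and all items answered changes.

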#### 13.3.1.4. Environmental Changes and Global Assessment of Symptom Severity

On a monthly basis subjects will provide information on changes to their home environment via six questions in the diary binder:

- Any changes to number of cats in your home?
- Have you been to a house in the last month where there is a cat?
- Significant change to the number of hours spent in a house with a cat?
- Have the cats in your home been spending more time outside?
- Any significant changes in your exposure to cat(s)?
- Any significant changes to your home furnishings?

The global assessment of symptoms is only applicable to subjects that no longer keep a cat. On a monthly basis, if these subjects had some unplanned exposure to a cat in normal daily life, the subject will rate his/her symptoms in the following categories:

- Absent
- Mild, Barely noticeable
- Moderate, Annoying/troublesome

---

Document: CP007A SAP.docx  
Author: [name]

Version Number: V 2.0  
Version Date: 23 Feb 2017

Template No: CS\_TP\_BS016 – Revision 3  
Effective Date: 01May2012

Reference: CS\_WI\_BS005

- Severe, Very annoying/Very troublesome

#### 13.3.1.5. Monthly Days Off School/Work

On a monthly basis subjects will enter in their dairy binders the total number of days that either school or work was missed due to allergic Rhinoconjunctivitis symptoms during the past month.

#### 13.3.1.6. Hospital/Doctor Office Visits

On a monthly basis subjects will enter in their dairy binders the dates of doctor/hospital visits as well as the date of entry and discharge from the hospital, if applicable, during the past month.

The length of stay in hospital per hospital visit is to be calculated as follows:

- Length of Stay (weeks) = [(Date of discharge – Date of entry + 1)] / 7.

### 13.3.2. ANALYSIS OF EXPLORATORY EFFICACY VARIABLES

The exploratory efficacy analysis is to be performed for the FAS.

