## 4. PLANNED ANALYSES

There are four planned unblinded interim analyses.

The first analysis of the data is to be performed on the first year's data after all subjects have either

- Completed their year 1 annual assessment in CP007A
- Discontinued prior to their year 1 annual assessment
- Progressed beyond their year 1 annual assessment regardless of the completion of the assessment

Additional analyses of the second, third and fourth year in the study are to be performed for each relevant year based on the same criteria as above. Analysis of the later years will only be performed if there was a positive outcome in the previous years.

The Quintiles study team, including those responsible for creating the programs to produce the outputs for each analysis, will remain blinded. Once the programs have been produced by the blinded Quintiles study team, these programs are to be sent to an independent statistician at a different geographical location than the blinded team, who will apply the randomisation schedule and provide Circassia with a set of unblinded outputs each year.

Details on independent unblinded team members within Quintiles to perform the analysis and members within Circassia authorised to receive unblinded outputs are specified in a separate Unblinding Plan document.

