### 5.2. FULL ANALYSIS SET [FAS]

The Full Analysis Set (FAS) will consist of all subjects who are consented into the study and have at least one day of symptom scores and rescue medication use recorded during the annual Allergy Evaluation Period of CP007A. Subjects are to be listed and summarised by the treatment they were randomised to in study CP007. The FAS population is to be re-assessed for each analysis year to account for subject drop-outs during each year.

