### 12.1. MEDICATION USE OUTSIDE ANNUAL ALLERGY ASSESSMENT PERIOD

Medication use outside of the annual Allergy Assessment Period is to be presented for the SAF population.

Medications outside of the annual Allergy Assessment Period are defined as any medications entered on the Medicines page of the monthly diary binder.

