## 13. EFFICACY OUTCOMES

### 13.1. PRIMARY EFFICACY

#### 13.1.1. PRIMARY EFFICACY VARIABLE & DERIVATION

The primary efficacy variable is the daily Combined Score (CS) of the 3-week annual Allergy Assessment Period completed after Year 1 to Year 4 in the subject's annual assessment diary binder.

The daily Total Rhinoconjunctivitis Symptom Score (TRSS) and the daily Rescue Medication Score (RMS) are to be combined and a daily CS is to be calculated for each subject as follows:

- $CS = (TRSS / 8) + RMS$

For the primary analysis, for each subject the mean of the daily non-missing CS during the annual Allergy Assessment Period is to be calculated as follows:

- $Sum(\text{Day 1 CS to Day 21 CS}) / \text{Number of non-missing days}$

The mean CS is to be calculated over the 21 days of the annual Allergy Assessment Period for each subject based on the data available for the non-missing days if a subject does not complete the whole annual assessment period.

The TRSS is the sum of eight individual TRSS symptom scores, namely runny nose, sneezing, blocked nose, itchy nose, itchy eyes, watery eyes, red eyes and sore eyes. All symptoms are reflective over the previous 24 hours.

For each symptom, the subject will rate (on a daily basis for the duration of the Allergy Assessment Period) the severity as follows:

0 = absent

1 = mild, barely noticeable

2 = moderate, annoying/troublesome

3 = severe, very annoying/very troublesome

The TRSS will have a range of 0 to 24. The TRSS on each day is to be calculated as follows:

TRSS = Runny Nose + Sneezing + Blocked Nose + Itchy Nose + Itchy Eyes + Watery Eyes + Red Eyes + Sore Eyes.

---

Document: CP007A SAP.docx

Author: [name]

Version Number:

V 2.0

Version Date:

23 Feb 2017

Template No: CS\_TP\_BS016 – Revision 3

Reference: CS\_WI\_BS005

Effective Date: 01May2012

Copyright © 2012 Quintiles Transnational Corp. All rights reserved.

The contents of this document are confidential and proprietary to Quintiles Transnational Corp. Unauthorized use, disclosure or reproduction is strictly prohibited.

Allergy medications are to be provided to subjects to be used according to a pre-specified Allergy Medication Plan (Appendix 1 in Protocol). The use of allergy medications are to be scored based on Didier (Didier *et al*, 2009) as follows:

- RMS = 0; no allergy medication used per day
- RMS = 0.5; at least one dose of antihistamine eye drops used per day

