#### 13.3.2.6. Hospital/Doctor Office Visits

The total number of hospitalisations as well as the number and percentage of subjects hospitalised are to be presented for each monthly assessment and treatment arm.

The length of stay of visits is to be summarised by descriptive statistics (n, mean, SD, median, minimum and maximum) for each monthly assessment and treatment arm.

Similarly, the total number of doctor visits as well as the number and percentage of subjects with any visit to the doctor are to be presented for each monthly assessment and treatment arm.

---

Document: CP007A SAP.docx

Author: [name]

Version Number:

V 2.0

Version Date:

23 Feb 2017

Template No: CS\_TP\_BS016 – Revision 3

Reference: CS\_WI\_BS005

Effective Date: 01May2012

Copyright © 2012 Quintiles Transnational Corp. All rights reserved.

The contents of this document are confidential and proprietary to Quintiles Transnational Corp. Unauthorized use, disclosure or reproduction is strictly prohibited.

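### The monthly-diary endpoints are summarised in a yearly FAS that depends on the later annual diary, so monthly records from subjects who leave or skip that diary are omitted from the year's tables

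*SAP*

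**What the plan says.** SAP 13.3.2 sets one population for every exploratory endpoint: "The exploratory efficacy analysis is to be performed for the FAS". Sections 13.3.2.4 to 13.3.2.6 do not override it. These endpoints come from the monthly diary and are tabulated by month. For hospital stays, for example, "the number and percentage of subjects hospitalised are to be presented for each monthly assessment and treatment arm".

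Under SAP 5.2, FAS members must be consented and "have at least one day of symptom scores and rescue medication use recorded during the annual Allergy Evaluation Period of CP007A". Membership is annual: "The FAS population is to be re-assessed for each analysis year to account for subject drop-outs during each year". SAP 13.1.1 places the diary that decides membership late in the sequence, as the "annual Allergy Assessment Period completed after Year 1 to Year 4 in the subject's annual assessment diary binder".

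SAP 4 expects two groups who may have monthly data but no annual diary for the year. Its criteria for the first analysis, which carry over to later years, include subjects who "Discontinued prior to their year 1 annual assessment" and subjects who "Progressed beyond their year 1 annual assessment regardless of the completion of the assessment".

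A wider set already exists. ENR (SAP 5.1) is everyone consented, by randomised arm, which is the same membership as the protocol's ITT population (Protocol 7.3.1). For the Medicines page of the monthly binder the SAP uses neither ENR nor the FAS: "Medication use outside of the annual Allergy Assessment Period is to be presented for the SAF population".

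**The concern.** A month-1 record of a doctor visit or a lost school day is complete when it is entered and uses nothing from the 3-week diary. Under SAP 13.3.2 it counts only if the same subject later supplies a valid day in that diary. A subject who reports seven months and then withdraws is missing from all seven of those months' tables. Protocol 6.2.4 gives such a subject a withdrawal visit and a withdrawal page but no 3-week diary, so a mid-year leaver would ordinarily not qualify for that year.

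This is selection on a post-randomisation event as well as lost precision. If leavers have more visits, missed days or worse symptoms, the monthly tables understate burden. If leaving differs by arm, they can hide or create a difference. Protocol 7.4.2 expects missing data to matter and promises to explore it, but SAP 7.3 sends missing efficacy data only to 13.1.3, which covers the Combined Score. Nothing in the plan examines these exclusions.

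**Working it through.** **1. The plan's own figures.** Protocol 7.2 gives a difference of 0.525, SD 1.29 and two-sided alpha 0.025. Power = Φ(0.525 / (1.29 × √(2/n)) − 2.241).
- n = 266 per arm: 0.525/0.1119 = 4.693, so Φ(2.452) = 99.3%.
- n = 130 per arm: 0.525/0.1600 = 3.281, so Φ(1.040) = 85.1%.

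Both of the protocol's minimum power statements (99% and 80%) hold. They are power scenarios for the Combined Score. Neither is a withdrawal forecast, and no withdrawal rate is stated anywhere.

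**2. Assumptions for the illustration.** w is the share of a year's starters who leave before the annual diary, with exits spread evenly and no skippers. I take w = 5%, 10% and 16.4%. The last is the constant annual loss that would link the two scenarios: 1 − (130/266)^(1/4) = 1 − 0.836 = 0.164. RR is the leavers' monthly event rate relative to stayers. RR has no source in the documents.

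**3. Share of collected person-months omitted.** Leavers contribute half a year on average, so the share is 0.5w / (1 − w + 0.5w).
- w = 0.05: 0.025/0.975 = 2.6%
- w = 0.10: 0.050/0.950 = 5.3%
- w = 0.164: 0.082/0.918 = 8.9%

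Counting only whole monthly diaries (mean 5.5 per leaver) gives 2.4%, 4.8% and 8.2%. Skippers raise the share. With 10% leaving and 5% skipping but completing all 12 months, it is (0.10 × 5.5 + 0.05 × 12) / (0.85 × 12 + 1.15) = 1.15/11.35 = 10.1%.

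**4. Understatement of the mean.** Set the stayers' rate to 1, so the FAS mean is 1.
- Year average, FAS mean over mean of all reported months: (1 − 0.5w) / (1 − w + 0.5w·RR).
- Month 1, if every leaver reports it: 1 / (1 − w + w·RR).

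| w | RR | Year average | Month 1 |
|---|---|---|---|
| 0.05 | 2 | 0.975 (2.5% low) | 0.952 (4.8% low) |
| 0.10 | 2 | 0.950 (5.0% low) | 0.909 (9.1% low) |
| 0.164 | 1.5 | 0.957 (4% low) | 0.924 (8% low) |
| 0.164 | 2 | 0.918 (8% low) | 0.859 (14% low) |
| 0.164 | 3 | 0.848 (15% low) | 0.753 (25% low) |

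The gap is largest in month 1. It shrinks towards zero by month 12, when few leavers are still reporting.

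**5. Unequal loss between arms (assumed: 10% active, 22.8% placebo, RR 2, stayers equal).** The FAS ratio is 1.00. Over the year's reported months, active is 1.00/0.950 = 1.053 and placebo is 1.00/0.886 = 1.129, a ratio of 0.93. In month 1 it is (0.90 + 0.20)/(0.772 + 0.456) = 0.90.

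**The case against.** The case for leaving the plan alone has real force.

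- **The bar is low and the outputs are minor.** One valid day is enough for the FAS. Protocol 6.2.2 and 6.2.3 provide reminders and an on-site visit just before the diary. Days off and visits are descriptive, and the one p-value is exploratory and outside the Bonferroni-Holm procedure. This stands and limits the impact.
- **Some of the information appears elsewhere.** Unplanned overnight hospitalisation meets the SAE definition (Protocol 6.4.2) and is summarised in the safety population, as are monthly medicines. This also stands, but it does not cover doctor visits, lost days or cat-exposure ratings.
- **The remedy is not free of selection.** A month-11 table loses earlier leavers under either rule, and a fixed yearly cohort gives way to one that changes by month. That is true, but responders to a given month are not also filtered by a later event.

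A reader might also infer more than the documents support:

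- **That the data are thrown away.** They are left out of summaries; nothing says they are deleted.
- **That the sponsor expects a fall from 266 to 130 per arm.** Protocol 7.2 says only that some subjects will withdraw and that power holds at 130.
- **That the month-1 figures describe the year.** They are the extreme month.
- **That the CMH test certainly excludes these subjects.** SAP 13.3.2.4 describes it as covering all subjects who have stopped keeping a cat, which could be read more widely than the FAS. Its place under 13.3.2 makes the FAS the natural reading, not the only one.
- **That using the safety set for the Medicines page contradicts 13.3.2.** A medication summary and an efficacy summary may properly use different sets. The point shows only that monthly data can be tabulated without the annual-diary condition.

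**Conclusion.** The point holds. As written, the monthly tables in SAP 13.3.2.4 to 13.3.2.6 are conditional on a later post-randomisation event, and the SAP itself foresees the subjects this leaves out. The CMH test is probably conditional in the same way.

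The documents do not allow the size to be estimated. Under the stated illustration (even exits, no skippers, 5% to 16.4% annual loss), about 3% to 9% of a year's collected person-months are omitted. With leavers at twice the event rate, the year-average mean is about 2.5% to 8% low. If leavers do not differ from stayers, the cost is precision only. Distortion of the arm comparison needs leaving, or the leavers' event rates, to differ by arm, and the documents neither show nor exclude that.

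Two limits apply. A subject left out of one year's FAS may re-enter in a later year, but the omitted year's months do not return to that year's tables. Enrolment may occur at any time after CP007 (Protocol 6.2.1), so the annual diary need not follow a full 12 monthly diaries for everyone. The effect is confined to exploratory or descriptive outputs. The primary analysis and the success criterion are untouched.

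**What to change.** In SAP 13.3.2:

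- Present 13.3.2.4 to 13.3.2.6 in ENR subjects, by randomised arm, with that month's assessment available, whether or not the annual diary was completed.
- Keep endpoint-specific conditions within that set, such as the denominator in 13.3.2.4 of those who reported visiting a house with a cat.
- State that the CMH test uses the same population, which also removes the ambiguity in its wording.
- Keep the FAS for the PSQI, ACQ and WPAI:CIQ-AS, which are collected at the annual evaluation, and show the FAS versions of the monthly tables as supportive.
- For consistency, apply the same population to the monthly asthma-progression tables in 13.2.2.5, which come from the monthly diary and are also tied to the FAS through 13.2.2.

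The cost is SAP wording and a changed population flag in the affected tables. No new data are needed. The downside is that N will vary by month and will differ from N in the annual tables, so each monthly table should show its own denominator.
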